4. Subjects with a history of clinically significant hemolysis, anemia, or enteritis (regional enteritis, ulcerative colitis, pseudomembranous colitis, antibiotic-associated colitis)
5. Subjects with allergy or sensitivity to the study drug or its components
6. Subjects who have not complied with the proper wash-out periods:
 - a. Topical anti-inflammatory medications, salicylic acid, corticosteroids, antibiotics, antibacterials, peroxide-containing products, or retinoids within 2 weeks of baseline
 - b. Systemic antibiotics, corticosteroids, antimalarials or oral dapsone within 4 weeks of baseline

- c. Other anti-acne medication, including isotretinoin or spironolactone, within 6 months of baseline
 - d. Chemical peels or other facial acne procedures (laser therapy, light therapy) within 3 months of baseline
 - e. Treatment with botulinum toxin of any serotype in the face within 6 months of baseline
 - f. Estrogens/Birth control pills must have been started ≥ 90 days prior to baseline and use must be continued during the study without alteration or discontinuation.
7. Pregnant or breastfeeding.
 8. Subjects with evidence of alcohol or substance abuse.
 9. Use of any investigational drug within 4 weeks prior to randomization, or 5 pharmacokinetic/pharmacodynamic half-lives, if known (whichever is longer).

c) Number of Subjects

Up to 40 subjects with acne vulgaris will be screened with a goal of 20 total subjects randomized. All 20 randomized subjects are expected to complete all study procedures. Individuals who provide informed consent and fail to meet all of the inclusion and exclusion criteria during the initial evaluation will be considered a “screening failure.”

d) Study Timelines

The study will consist of 6 in-person visits and one phone visit (7 total visits) over up to 28 weeks (4 week screening period plus 24 weeks enrolled in study). Study visits will be conducted at Screening (Visit 1), Baseline (Visit 2, Week 0), Week 4 (Visit 3), Week 8 phone visit (Visit 4), Week 12 (Visit 5), Week 18 (Visit 6), Week 24 (Visit 7).

Enrollment will occur over a 24-36 month period from January 2018 to December 2020. The study is anticipated to be completed by December 2021.

e) Endpoints

Primary Endpoint:

1. Mean change from baseline to week 12 in Global Acne Assessment Score (GAAS)

Secondary Endpoints:

1. Change from baseline in Global Acne Assessment Score (GAAS) at week 4, 18, and 24.

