6. N/A
7. N/A

8. Adverse events will be graded using the Common Terminology Criteria for Adverse Events (CTCAE).
9. The study will be conducted in compliance with regulatory requirements and Good Clinical Practice. Quality control will be applied to each stage of data handling to ensure that data are accurate, reliable and processed correctly.
10. Should a temporary or permanent suspension of our study occur, the occurrence will be reported to the PPHS, sponsor, and IRB.

Part II. Data Monitoring Committee/Data Safety Monitoring Board (DMC/DSMB)

Not applicable

j) Withdrawal of Subjects

When an individual who has signed the ICF is not enrolled in the study or withdraws/is withdrawn prior to completing the study, the reason is to be documented on the Discontinuation/Completion Form (or equivalent) and in the final study report. Reasons for subject withdrawal may include:

- Not enrolled (e.g. fails to meet inclusion/exclusion criteria, chooses not to enroll, etc.)
- Participant is determined to be ineligible after enrollment
- Subject's choice to withdraw
- Investigator terminated (e.g. noncompliance, etc.)
- Adverse Event
- Pregnancy
- Lost to follow-up
- Other

Subjects may withdraw from the trial at any time at their request, or they may be withdrawn at any time at the discretion of the Sponsor, PI, or designee for safety, behavioral, or administrative reasons. Subjects may be withdrawn from this study without their consent if the research study is being stopped; or if the instructions of the study team have not been followed.

If a subject does not return for a scheduled visit, *three documented attempts will be made to contact the subject in order to establish the reason for withdrawal, and* the outcome will be documented. The PI or designee should inquire about the reason for withdrawal, request that the subject return for a final visit, if applicable, and follow-up with the subject regarding any unresolved adverse events.

Should a subject withdraw from the trial and also withdraw consent for disclosure of future information, no further evaluations should be performed and no additional data should be collected. The PI and staff may retain and continue to use any data collected before such withdrawal of consent. Removed or withdrawn subjects will not be replaced.

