Study drug is stored in a combination-locked room accessible only by clinical trials personnel. All study materials should be stored at room temperature (59°-77°F), and the Site is responsible for maintaining temperature logs. All study products received and dispensed will be inventoried and accounted for throughout the study. The investigator must maintain adequate records documenting the receipt, use, loss, or other disposition of the products on the Product Accountability Log. The log must identify the investigational product and account for its disposition by subject, including specific dates and quantities dispensed and returned. The log must be signed by the individual who dispensed/retrieved the study product and copies must be provided to the sponsor for inclusion in the Trial Master File.

At the completion of the study, all units of product dispensed (whether empty or containing unused product) must be collected by the Site and returned, along with un-dispensed product, to the Sponsor. Any container not returned by the Site must be accounted for in writing.

k) Statistical Analysis Plan

The adverse events will be tabulated according to their date of onset, duration, severity and relationship to the treatment. We will build Clopper-Pearson 90% confidence intervals for the proportion of adverse events considering their aggregation and stratification (e.g., by severity).

Sample Size Considerations

A sample size of $n=20$ subjects allows $>90\%$ power at 5% significance level for a two-sided paired t-test to detect at week 12 a minimum change in GAAS from baseline of 1 grade point. This calculation was performed in G*Power and it assumes a mean GAAS of 3.5 at baseline and a maximal standard deviation of 0.513.

Analysis of primary Endpoint

The primary analysis will apply a two-sided paired t-test to assess the significance of the change in GAAS from baseline to week 12. However, GAAS is an ordinal measurement and, for this reason, we will also apply a Generalized Linear Mixed-effects Model (GLMM) to assess the significance of the changes in GAAS after including potential covariates.

Analysis of secondary Endpoints

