At each time point, the changes from baseline in ordinal secondary endpoints GAAS, PAHPI, MI, the proportion of subjects with a score of 0 or 1 on ASIS “dark spot,” the proportion of subjects with $GAAS < 2$ will be presented in frequency tables. The (i,j) entries in the tables are counts of subjects in category i at baseline that moved to category j at that time point. A high frequency of counts falling off the main diagonal of the table is evidence in favor of a significant treatment effect. Similarly, to the primary endpoint, we will apply a two-sided paired t-test to assess the significance of changes from baseline in each outcome. We will apply the Bonferroni correction to adjust for the multiplicity of tests. In parallel, we will test pre vs. post differences in these ordinal outcomes with the Wilcoxon Signed Rank test. Discrepancies between the parametric and non-parametric approaches will be discussed on a case basis. In addition to this approach, we will fit an ordinal logit model, including all available time points, age, and gender as covariates.

The changes from baseline in lesion counts (inflammatory, non-inflammatory, and their aggregation) will be assessed with the two-sided paired t-test followed by Bonferroni correction. A Generalized Linear Mixed Model (GLMM) will be fitted to model the count of lesions as the dependent variable, time and inflammation as fixed effects, age, and gender as covariates. In this framework, we will include random intercept and slope for each subject’s trajectory. The contrasts will reveal differences between time points and treatment effect in inflammatory vs. non-inflammatory lesions.

Missing Data and Outliers

Missing data in the longitudinal data analysis will be handled by the mixed-effects approach which performs an appropriate adjustment of the coefficients’ degrees of freedom for each fitted model. We do not foresee issues with outliers due to the endpoints’ measurement level, most of them being ordinal.

Reference:

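### The primary paired t-test uses only subjects with a week-12 GAAS, the missing-data rule reaches that endpoint only through a loosely specified supportive model, and no sensitivity analysis for missing data is planned

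*Combined protocol and SAP*

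**What the plan says.** The primary endpoint (section e) is the mean GAAS change from baseline to week 12. Under Analysis of primary Endpoint, section k states: "The primary analysis will apply a two-sided paired t-test to assess the significance of the change in GAAS from baseline to week 12". The next sentence adds a generalized linear mixed-effects model (GLMM) for GAAS, because the scale is ordinal and to bring in covariates. It does not list the visits that enter the model or say which result prevails if the two differ.

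Under Missing Data and Outliers, the rule is: "Missing data in the longitudinal data analysis will be handled by the mixed-effects approach". The justification follows: "which performs an appropriate adjustment of the coefficients", referring to their degrees of freedom.

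Section c expects every one of the 20 subjects to finish all procedures. Section j nevertheless lists reasons for withdrawal, among them the subject's own choice, noncompliance, adverse events and loss to follow-up, and says: "Removed or withdrawn subjects will not be replaced". No text available for this review defines an analysis set, a rule for a missing week-12 GAAS in the t-test, or a sensitivity analysis for missing data.

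**The concern.** A paired t-test needs both values, so a subject without a week-12 GAAS drops out of the primary analysis by default, and the plan does not say so. The paired t-tests and Wilcoxon tests of the secondary endpoints have the same gap.

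The rationale in the missing-data rule is also mistaken. A likelihood-based mixed model accommodates missing visits by using all the observed ones. It is valid if data are missing at random and the model is adequate. A degrees-of-freedom adjustment changes tests and intervals; it does not remove bias from selective loss.

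This matters because the trial is single-group and open-label, so the mean change is its main efficacy result. There is no control arm in which a similar pattern of loss might be seen.

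**Working it through.** Improvement is written as a positive number of grades throughout.

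**1. The plan's own figure.** Sample Size Considerations gives n = 20, a change of 1 grade, SD 0.513, two-sided 5% and power above 90%. It does not say whether 0.513 is the SD at one visit or the SD of the change.
- As the SD of the change: noncentrality = (1/0.513) × √20 = 8.72; power is above 99.9%.
- As a per-visit SD, uncorrelated readings: SD of change = 0.513 × √2 = 0.725; power 99.99%.
- As a per-visit SD, extreme correlation of -1: SD of change = 2 × 0.513 = 1.026; power 98.5%.

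The stated power reproduces. With 14 completers it is still 99.7% (correlation 0) or 92.0% (correlation -1), so dropout is not a power problem here.

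**2. Leavers with no change.** Assume completers improve by 1.0 and k of 20 leave unchanged. The t-test reports 1.0; the mean for all 20 is (20 - k)/20.

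| k missing | Mean, all 20 | Overstatement | Relative to all-20 mean |
|---|---|---|---|
| 2 | 18/20 = 0.90 | 0.10 | 0.10/0.90 = 11% |
| 4 | 16/20 = 0.80 | 0.20 | 0.20/0.80 = 25% |
| 6 | 14/20 = 0.70 | 0.30 | 0.30/0.70 = 43% |

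If leavers had instead improved by 0.5, the all-subject means would be 0.95, 0.90 and 0.85, and the overstatement would halve.

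**3. Does significance survive?** Take k = 6 and completer SD 0.513.
- Sum of squares = 13 × 0.513² + 14 × 0.30² + 6 × 0.70² = 3.42 + 1.26 + 2.94 = 7.62.
- SD = √(7.62/19) = 0.633; standard error = 0.633/√20 = 0.142.
- Mean 0.70, t = 4.94, 95% CI 0.40 to 1.00, p about 0.0001.

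**4. Dropout that depends on week-4 response (missing at random).** Assumptions, none from the documents: true change 0.8, SD 0.7, week-4/week-12 correlation 0.6, and logistic dropout more likely after a poor week-4 response. The completer bias is 0.6 × 0.7 × d = 0.42d, where d is how far the completers' mean week-4 change lies above that of the whole group, in SDs.
- With a log-odds slope of 1.0 per SD, simulation gives 0.06, 0.09 and 0.12 grade at 16%, 25% and 35% missing (d = 0.06/0.42 = 0.14, 0.09/0.42 = 0.21, 0.12/0.42 = 0.29).
- A set of runs with 13 to 35% missing gave 0.05 to 0.16 grade. Slopes from 0.5 to 1.5 with 13 to 37% missing gave 0.03 to 0.17.
- An estimator that also uses the week-4 data left a bias of about 0.001.
- If the SD of the change were 0.513, the bias would scale by 0.513/0.7 = 0.73, so 0.05 to 0.16 becomes about 0.04 to 0.12.

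**The case against.** The strongest reply is that the plan already includes a mixed model for the same primary endpoint, in the sentence after the t-test. The missing-data rule therefore does reach that endpoint. This stands, and it rules out a reading that a reader might otherwise take: that the plan has no method for missing GAAS data. What remains is a gap in ranking and specification. The GLMM is supportive, its visits are not given, and it is justified by the ordinal scale, not by missing data. The ordinal logit model with all time points belongs to the secondary endpoints and is not described as having random effects.

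Second, nothing in the documents shows that poor responders would leave. Section c expects full completion, and section j provides for three contact attempts and a request to attend a final visit. This also stands. A reader might infer that the trial will overstate efficacy; the documents support only the conditional statement.

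Third, the near-zero bias of the week-4 estimator follows by construction, because dropout was simulated to depend on week 4. This is correct: it shows what the model can do under missing at random, not that missing at random holds. Nor is the mixed model shown to remove the no-change bias of step 2.

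Fourth, correcting the degrees-of-freedom sentence alone would alter no estimate. That is true. It is a wording repair, useful because it makes the assumption explicit.

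Finally, week 8 is a phone visit without GAAS, so anyone who leaves before week 12 contributes at most one post-baseline score. An unstructured covariance over five visits has 5 × 6/2 = 15 parameters, for 20 subjects. These are real limits on the remedy and argue for a simpler covariance structure.

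**Conclusion.** The point holds in a limited form. The primary estimate is a completer estimate by default, the missing-data rule touches the primary endpoint only through an underspecified supportive model, and no sensitivity analysis covers dropout that is not at random. If poor early responders leave before week 12, improvement is overstated by roughly 0.05 to 0.16 grade with 13 to 35% missing at random. It is overstated by 0.10 to 0.30 grade if 2 to 6 of 20 leave unchanged and completers improve by 1.0. For comparison, the trial is sized "to detect at week 12 a minimum change in GAAS from baseline of 1 grade point". Every dropout rate and pattern here is assumed, and the bias reverses if good responders leave.

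It would be tempting to conclude that a significant primary result could be an artefact of dropout. The figures do not support that: with 6 of 20 set to no change, the interval still excludes zero by a wide margin. The issue is the size of the reported effect. This is an inexpensive improvement worth making, not a fatal flaw.

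**What to change.** 1. Take the week-12-minus-baseline estimate from a likelihood-based mixed model that includes all treated subjects and all GAAS visits (weeks 0, 4, 12, 18 and 24) as categorical time, with a parsimonious covariance structure and small-sample degrees of freedom. With no missing visits, a linear version gives the same point estimate as the paired t-test. At minimum, specify the planned GAAS GLMM in this way and report it beside the t-test. If that model is ordinal, also report its implied mean change in grades so that the two can be compared.
2. Label the paired t-test a completer analysis and report how many subjects it omits.
3. Add one sensitivity analysis with missing week-12 GAAS set to no change, because the mixed model does not remove bias from non-random dropout.
4. Replace the degrees-of-freedom rationale with a statement of the missing-at-random assumption.

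The cost is SAP wording and a little programming; the schedule already collects GAAS at these visits. The downside is reliance on missing at random and on a covariance model fitted in 20 subjects, with little post-baseline information on early leavers. A linear model also treats GAAS as continuous, as the t-test already does.
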